5.1.1 Study duration per subject

For each subject, the maximum total study duration can be up to 93 days (not withstanding visit windows), including the 30-day Safety Follow-Up Period. Each subject's participation in the study begins with a 7-day Baseline Period (no administration of study medication). Each subject's maximum total duration of study medication administration in SP0967 can be up to 55 days. This includes a 20-day Titration Period, a 7-day Maintenance Period, a 12-day Transition Period (for subjects who plan to enter the open-label extension study [EP0034]) and/or up to a 16-day Taper Period (for subjects who will not be entering EP0034).

The end of the study is defined as the date of the last visit of the last subject in the study.

5.1.2 Planned number of subjects and sites

A total of approximately 244 subjects (122 subjects per treatment arm) are planned to be randomized. Approximately 50% of the 244 randomized subjects should be <2 years of age. Of these (n=122), every attempt will be made to enroll a minimum target of 20% (n=25) of subjects in each of the 3 age categories: ≥ 1 month to <6 months, ≥ 6 months to <1 year, and ≥ 1 year to <2 years.

Every attempt will be made to enroll subjects in the following age categories as detailed below:

- ≥ 1 month to < 6 months of age (≥ 25 subjects)
- ≥ 6 months to < 1 year of age (≥ 25 subjects)
- ≥ 1 year to < 2 years of age (≥ 25 subjects)
- ≥ 2 years to < 4 years of age (≥ 20 subjects)

Approximately 140 sites are planned in order to recruit the required subjects; additional sites will be added if deemed necessary.

5.1.3 Anticipated regions and countries

The study will be conducted in North America, Europe, Asia Pacific, and Latin America with possible extension to other countries and regions. A target of approximately 30% of the randomized subjects should consist of subjects originating from sites in North America and Europe.

5.2 Schedule of study assessments

A tabular schedule of study procedures for the Baseline and Treatment Periods is presented in [Table 5-1](#). A tabular schedule of study procedures for the Transition Period is presented in [Table 5-2](#). A tabular schedule of study procedures for the Taper and Safety Follow-Up Periods is presented in [Table 5-3](#).

Table 5-1: Schedule of study assessments (Baseline and Treatment Periods)

Assessment	Baseline Period (7 days)				Treatment Period (27 days)							UV ^a		
	V1	V2	V2	V2	V3	T1	V4	T2	V5	T3	Maintenance Period (7 days)			
Study Day	-7	-3 ^b	-2	-1	1	5	9	13	17	20	24 ^b	25	26	27
Informed consent	X													
Demographics ^c	X													
Inclusion/exclusion criteria	X	X			X									
Medical history	X													
Seizure history/count	X													
Concomitant medications	X ^d	X	X	X	X	X	X	X	X	X	X	X	X	X
Concomitant AEDs	X ^e	X	X	X	X	X	X	X	X	X	X	X	X	X
VNS assessment ^f	X	X									X			X
Physical examination (complete)	X													X
Physical examination (brief)		X					X		X		X			
Vital signs (including BP and pulse rate) ^g	X	X					X		X		X			X
Body weight	X	X					X		X					X
Height	X													X
Head circumference	X													X
Neurological examination (complete)	X													X
Neurological examination (brief)							X				X			
ECG (12-lead) ^h	X				X ^g				X					X

Table 5–1: Schedule of study assessments (Baseline and Treatment Periods)

Assessment	Baseline Period (7 days)							Treatment Period (27 days)							UV ^a	
	V1	V2			V3			Titration Period (20 days)			Maintenance Period (7 days)					
Visit							V1	T1	V4	T2	V5	T3	V6/ET			
Study Day	-7	-3 ^b	-2	-1	1	5	9	13	17	20	24 ^b	25	26	27		
Video-EEG ⁱ		X	X	X	X							X	X	X		
Rescue medication ^j		X	X	X	X							X	X	X		
Clinical chemistry/hematology	X													X		
LCM plasma concentration									X					X		
Clinical GIC														X		
Caregiver's GIC														X		
Contact IXRS	X								X					X		
Randomization																
Dispense study medication									X					X		
Return study medication									X					X		
Dosing instructions ^l						X		X				X				
AE reporting	X	X	X	X	X	X	X	X	X	X	X	X	X	X		
Withdrawal criteria		X		X	X	X	X	X	X	X	X	X	X	X		
Healthcare resource use					X									X		
Bayley-III scales ^m					X											
BRIEF-p ⁿ					X											

This document cannot be used to support any marketing authorization application and any extensions thereof.

Table 5-1: Schedule of study assessments (Baseline and Treatment Periods)

Assessment	Baseline Period (7 days)		Treatment Period (27 days)									
	V1	V2	V3	T1	V4	T2	V5	T3	Maintenance Period (7 days)			
Visit										UV ^a		
Study Day	-7	-2	1	5	9	13	17	20	24 ^b	25	26	27
PedsQL ^o			X									X
Achenbach CBCL ^p			X									

AE=adverse event; AED=antiepileptic drug; BP=blood pressure; BRIEF-P=Behavior Rating Inventory of Executive Function-Preschool Version; CBCL=Childhood Behavior Checklist; ECG=electrocardiogram; EEG=electroencephalogram; ET=Early Termination; GIC=Global Impression of Change; IXRS=interactive voice/web response system; LCM=lacosamide; PedsQL=Pediatric Quality of Life Inventory; T=Telephone Contact; UV=Unscheduled Visit; V=Visit; VNS=vagus nerve stimulation.

- ^a If an Unscheduled Visit is needed, then the assessments noted will be performed. Additional assessments may be performed at the investigator's discretion.
- ^b The Day -3 and Day 24 assessments should be conducted prior to the start of video-EEG monitoring. A maximum of 7 days may be added to the period between Visit 1 and 2 in the event that additional time is needed to access inpatient facilities to perform the video-EEG.
- ^c Demographics: date of birth, age group category, age in months and years, race, ethnicity, and gender. In countries where recording of complete date of birth is not permitted, only permitted data will be collected.
- ^d The concomitant medications recording will include any current medication intake as well as any medications taken ≤30 days prior to Visit 1.
- ^e The concomitant AED recording will include any current medication intake as well as any previous AED taken prior to Visit 1.
- ^f The VNS setting will be assessed as applicable.
- ^g Orthostatic assessments of BP and pulse rate will be assessed where it is feasible according to investigator judgment.
- ^h A 12-lead ECG (2 interpretable recordings) will be performed prior to any blood draws and vital signs assessment and, if possible, with the subject in the supine position for 5 minutes preceding the ECG recording. The second recording will be conducted approximately 20 to 30 minutes after the first recording. Electrocardiograms will be reviewed locally by the investigator, subinvestigator, or qualified designated reader and at a central ECG laboratory. The investigator may consult with the cardiologist at the central ECG laboratory to confirm the presence of a clinically significant ECG abnormality; however, it remains the responsibility of the investigator to decide whether an ECG finding is of clinical significance on the basis of the complete clinical picture and whether this finding influences the subject's participation in the study.
- ⁱ The video-EEG (up to 72 hours of continuous recording with every attempt to at least 48 hours of interpretable recording) will be conducted in an inpatient setting. Upon completion of the End-of-Baseline video-EEG (Visits 2 and 3), the investigator will assess the electrographic seizure count and confirm the selection criteria have been met. If the subject meets all selection criteria, including the requisite number of seizures based on the video-EEG data, the subject may be randomized at Visit 3. Assessment of video-EEG seizure count will be performed locally by the investigator, subinvestigator, or qualified designated reader for the purpose of both assessment of eligibility and study analyses. The End-of-Maintenance Period video-EEG will be done at Visit 6. Subjects who discontinue on or before Day 20 will not require a video-EEG.

Table 5–1: Schedule of study assessments (Baseline and Treatment Periods)

Assessment	Baseline Period (7 days)			Treatment Period (27 days)										
	V1	V2	V3	T1	T2	T3	Titration Period (20 days)			Maintenance Period (7 days)				
Visit	V1	V2	V3	T1	T2	T3	V4	V5	V6/ET		UV ^a			
Study Day	-7	-3 ^b	-2	-1	1	5	9	13	17	20	24 ^b	25	26	27

^j Additional assessment for changes in VNS or rescue medication taken within 24 hours prior to and until the end of the video-EEG monitoring.
^k Randomization and initial dispensing of study medication will occur at Visit 3 and after the completion of the video-EEG and confirmation that the subject has met selection criteria.

^l Dosing instructions will be provided to the caregiver(s) during the telephone contacts. At a minimum, AEs and tolerability should be discussed with the caregiver(s) in order to determine the next dose for the subject. See Section 7.2.1 for additional details on dosing options.

^m Investigators must make every attempt to administer the Bayley Scales of Infant and Toddler Development, Third Edition, for subjects who are <18 months of age who originate in English-speaking countries. The investigators may utilize trained pediatric psychologists or other appropriately skilled individuals to administer the scale.

ⁿ The BRIEF-P will be used only for subjects who are ≥2 years of age at Visits 3. BRIEF-P will be used only in countries where a translated version is available.

^o The version of the PedsQL used at Visit 3 should be consistent with the subject's age at Visit 3 and should be maintained for each subject for the duration of the study. The PedsQL will be used only in countries where a translated version is available.

^p The Achenbach CBCL/1½-5 will be completed by the parent(s)/legal representative(s)/caregiver(s) of subjects ≥ 18 months of age at Visit 3. The Achenbach CBCL will be administered only in countries where a translated version is available.

^q ECG at Visit 3 will be performed at the discretion of the investigator.

Table 5–2: Schedule of study assessments (Transition Period)

Assessments	Transition Period (12 days)		
	TV1	TT1	TV2 ^a
Study Day	32	36	40
Concomitant medications	X	X	X ^b
Concomitant AEDs	X	X	X ^b
VNS assessment ^c	X		X ^b
Physical examination (brief)	X		
Physical examination (complete)			X ^b
Vital signs (including BP and pulse rate) ^d	X		X ^b
Body weight	X		X ^b
Neurological examination (brief)	X		
Neurological examination (complete)			X ^b
ECG (12-lead) ^e			X ^b
Clinical chemistry/hematology			X ^b
Contact IXRS	X		X
Dosing instructions ^f		X	
Dispense study medication	X		
Return study medication	X		X
AE reporting	X	X	X ^b
Withdrawal criteria	X	X	X

AE=adverse event; AED=antiepileptic drug; BP=blood pressure; ECG=electrocardiogram; IXRS=interactive voice/web response system; TT=Transition Telephone Contact; TV=Transition Visit; VNS=vagus nerve stimulation

^a Transition Visit 2 will also serve as Visit 1 for EP0034.

^b The designated procedures will serve as the point of data for both TV2 in SP0967 and Visit 1 for EP0034.

^c Vagus nerve stimulation setting will be assessed as applicable.

^d Orthostatic assessments of BP and pulse rate will be assessed if it is feasible according to investigator judgment.

^e A 12-lead ECG (2 interpretable recordings) will be performed prior to any blood draws and vital signs assessment and, if possible, with the subject in the supine position for 5 minutes preceding the ECG recording. The second recording will be conducted approximately 20 to 30 minutes after the first recording.

^f Dosing instructions will be provided to the caregiver(s) during the telephone contacts. See Section 7.2.3 for additional details on dosing options.

Table 5–3: Schedule of study assessments (Taper and Safety Follow-Up Periods)

Assessments	Taper Period (8 to 16 days)		Safety Follow-Up Period (30 days) ^a	
	T4 ^b	Taper Visit ^c	Safety Follow-Up Clinic Visit Days in Study: FSM+14 (±2)	Safety Follow-Up Telephone Contact Days in Study: FSM+30 (-1/+3)
Study Day	32 ^d	36/40/44 ^{c,d}	50/54/58 ^d	66/70/74/93 ^d
Concomitant medications	X	X	X	X
Concomitant AEDs	X	X	X	X
VNS assessment ^e		X	X	
Physical examination (brief)		X		
Physical examination (complete)			X	
Vital signs ^f (including BP and pulse rate)		X	X	
Body weight		X	X	
Neurological examination (brief)		X		
Neurological examination (complete)			X	
ECG (12-lead) ^g		X ^h	X ^h	
Clinical chemistry/hematology		X ^h	X ^h	
Contact IXRS		X		
Dosing instructions ⁱ		X		
Return study medication		X		
AE reporting	X	X	X	X
Withdrawal criteria	X	X		

AE=adverse event; AED=antiepileptic drug; BP=blood pressure; ECG=electrocardiogram; FSM=Final Study Medication; IXRS=interactive voice/web response system; T=Telephone Contact; VNS=vagus nerve stimulation

^a The Safety Follow-Up Clinic Visit will be scheduled 14 days (±2 days) after the final dose of study medication. The Safety Follow-Up Telephone Contact will occur 30 days (-1/+3 days) after the final dose of study medication.

^b A telephone contact (T4) will be conducted at the end of the first taper step of the Taper Period.

^c Each subject will have only 1 Taper Visit. The Taper Visit will be scheduled at the end of the Taper Period (Day 36, 40, or 44), depending on dose level achieved (see Table 7-3).

^d The study day numbers provided are for subjects who complete the Maintenance Period and enter the Taper Period. The study day numbers provided do not apply to subjects who enter the Taper Period at other times. Day 66, 70, or 74 result from the administration of final study medication during the Taper Period whereas Day 93 would result from a subject progressing to the end of the Transition Period, but then not entering EP0034 and instead entering the Transition Period followed by the Taper Period.

^e VNS setting will be assessed as applicable.

^f Orthostatic assessments of BP and pulse rate will be assessed where it is feasible according to investigator

Table 5–3: Schedule of study assessments (Taper and Safety Follow-Up Periods)

Assessments	Taper Period (8 to 16 days)		Safety Follow-Up Period (30 days) ^a	
	T4 ^b	Taper Visit ^c	Safety Follow-Up Clinic Visit Days in Study: FSM+14 (±2)	Safety Follow-Up Telephone Contact Days in Study: FSM+30 (-1/+3)
Study Day	32 ^d	36/40/44 ^{c,d}	50/54/58 ^d	66/70/74/93 ^d

judgment.

^g A 12-lead ECG (2 interpretable recordings) will be performed prior to any blood draws and vital signs assessment and, if possible, with the subject in the supine position for 5 minutes preceding the ECG recording. The recordings should be made approximately 20 to 30 minutes apart.

[figure not shown]
^h The assessment will be required for subjects with a clinically significant abnormal value (clinical chemistry or hematology) or reading (ECG) at the previous clinic visit. For non-clinically significant abnormalities, repeat of these assessments is at the discretion of the investigator.

ⁱ Dosing instructions will be provided to the caregiver(s). See Section 7.2.3 for additional details on dosing options.

5.3 Schematic diagram

[figure not shown]
An overall schematic diagram for subjects entering EP0034 is provided in Figure 5–1. An overall schematic diagram for subjects not entering EP0034 is provided in Figure 5–2.

Figure 5-1: Subjects entering EP0034 open-label extension study

PBO=placebo; T=Telephone Contact; TT=Transition Telephone Contact; TV=Transition Visit; V=Visit

Figure 5-2: Subjects not entering EP0034 open-label extension study

^a Subjects progressing to the end of the Transition Period, but then not entering EP0034 and instead entering the Transition Period followed by the Taper Period would complete the Safety Follow-Up Period at Day 93. PBO=placebo; T=Telephone Contact; V=Visit

5.4 Rationale for study design and selection of dose

Epilepsy is a condition for which an improved benefit/risk ratio for medicinal products remains a challenge; this is especially true for pediatric patients. Based on the demonstrated efficacy and safety of LCM as adjunctive treatment in subjects aged ≥ 16 years of age, and the experience with other AEDs in pediatric subjects, it is likely that LCM will be an efficacious and safe treatment in the pediatric population with uncontrolled partial-onset seizures.

SP0967 is a Phase 3, multicenter, double-blind, randomized, PBO-controlled, parallel-group study to evaluate the efficacy and safety of LCM as adjunctive therapy in subjects ≥ 1 month to < 4 years of age with epilepsy who have uncontrolled partial-onset seizures.

Based on the currently available LCM pediatric PK, safety, and tolerability data from SP847 and SP1047, as well as on information available in the medical literature, the recommendations for SP0967 are as follows:

- Subjects must weigh ≥ 4 kg to < 30 kg at Visit 1.
- Feeding tube administration is permitted for subjects who are unable to swallow the oral solution.
- Titration should occur over a 20-day period; with LCM dose increased by 2mg/kg/day every 4 days until the target dose (LCM 8mg/kg/day to 12mg/kg/day, or matching PBO) is achieved. All subjects will start on a dose of LCM 4mg/kg/day or matching PBO at the start of the Titration Period.
- During the Titration Period, step-back titration by LCM 1mg/kg/day or LCM 2mg/kg/day will be permitted to allow subjects with reduced tolerability to remain in the study depending on tolerability (ie, based on investigator judgment and legal representative[s]/caregiver[s] feedback). If study medication is back titrated, the dose must never be lower than LCM 4mg/kg/day (or matching PBO) and must be maintained for ≥ 3 days (in order to reach steady state) before subsequent titration to a higher dose.
- During the Titration Period, subjects may also have the dose of study medication held steady or titrated to a higher dose. If study medication is titrated to a higher dose, the subject must remain on that dose for ≥ 4 days unless a step-back titration based on tolerability is required.
- The LCM dose should remain fixed over the Maintenance Period.

Based on US FDA and EMA requirements, 2 (co-) primary efficacy variables have been defined for this study based on electrographic partial-onset seizures with or without clinical correlate depending upon subject age. The primary efficacy variable will be the change in ADF of electrographic partial-onset seizures (US) or proportion of subjects experiencing $\geq 50\%$ reduction in their ADF of electrographic partial-onset seizures (EU) as measured on the End-of-Maintenance Period video-EEG compared to the End-of-Baseline Period video-EEG. At the request of FDA, a contingent primary efficacy variable has also been defined based on the percentage of subjects who discontinue early from the study prior to completing the End-of-Maintenance Period video-EEG. Contingent upon $> 10\%$ of subjects discontinuing early from the study, the primary efficacy parameter for the US will become identical to the primary efficacy parameter for the EU.

The endpoint not designated as primary will still be summarized as a secondary efficacy parameter.

6 SELECTION AND WITHDRAWAL OF SUBJECTS

6.1 Inclusion criteria

To be eligible to participate in this study, all of the following criteria must be met:

1. An Institutional Review Board (IRB)/Independent Ethics Committee (IEC) approved written Informed Consent form is signed and dated by the parent(s) or legal representative(s)/caregiver(s) (in accordance with local regulation).
2. Subject's parent(s) or legal representative(s)/caregiver(s) is considered reliable and capable of adhering to the protocol visit schedule or medication intake according to the judgment of the investigator.
3. Subject is male or female from ≥ 1 month (ie, 4 weeks after full term [37 weeks gestational age]) to < 4 years of age. For preterm infants < 1 year old, the corrected gestational age should be used when determining eligibility. The generally accepted definition of corrected gestational age, which is calculated by subtracting the number of weeks born before 37 weeks of gestation from the chronological age, will be used for this study.
4. Subject has a diagnosis of epilepsy with partial-onset seizures. The results of ≥ 1 prior EEG and ≥ 1 magnetic resonance imaging/computerized tomography scan should be consistent with this diagnosis.
5. Subject weighs ≥ 4 kg to < 30 kg at Visit 1.
7. Subject has experienced ≥ 2 partial-onset seizures with or without secondary generalization during each consecutive 7-day period during the 2 weeks prior to Visit 1.
- 8a. Subject has ≥ 2 partial-onset seizures with or without secondary generalization during the End-of-Baseline video-EEG. Electrographic seizures are defined as recognizable ictal patterns on an EEG involving ≥ 2 contiguous electrodes. The seizures are initiated as a unilateral or strongly asymmetric abnormal epileptiform discharge lasting a total of > 10 seconds.
9. Subject is on a stable (concurrently or sequentially) dosage regimen of 1 to 3 AEDs. The dosage regimen of concomitant AED therapy must be kept constant for a period of ≥ 2 weeks prior to Visit 1. A stable daily dosage regimen of a concomitant benzodiazepine (BZD) will be considered as a concomitant AED.
10. Vagus nerve stimulation is allowed and will not be counted as a concomitant AED. The VNS device must have been implanted for ≥ 6 months prior to Visit 1; device settings must be kept stable for ≥ 2 weeks prior to Visit 1 and kept stable during the Baseline, Treatment, and Transition Periods. Use of the VNS device magnet is allowed.
11. Subject is an acceptable candidate for venipuncture.

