5 STUDY DESIGN

5.1 Study description

SP0967 is a Phase 3, multicenter, double-blind, randomized, PBO-controlled, parallel-group study to evaluate the efficacy and safety of LCM 8mg/kg/day to LCM 12mg/kg/day as adjunctive therapy in subjects ≥ 1 month to < 4 years of age with epilepsy with partial-onset seizures.

Primary and secondary efficacy variables will be based on video-EEGs (up to 72 hours of continuous recording with every attempt to obtain at least 48 hours of interpretable recording). The video-EEGs will be conducted in an inpatient setting. Assessment of video-EEG seizure count will be performed locally by the investigator, subinvestigator, or qualified designated reader for the purpose of both assessment of eligibility and study analyses.

Baseline Period

At Visit 1 (Day -7), subjects who meet the selection criteria will begin a 7-day Baseline Period (Day -7 to Day -1). In the event that additional time is needed to access inpatient facilities to perform the video-EEG, a maximum of 7 days may be added to the period between Visit 1 and 2. From Visit 2 (Day -3 to Day -1) to Visit 3 (Day 1), an End-of-Baseline Period video-EEG will be performed.

After completion of the End-of-Baseline video-EEG at Visit 3, subjects who meet the selection criteria will be randomized in a double-blind manner to 1 of 2 parallel treatment arms: LCM or PBO in a 1:1 ratio.

Titration Period

Subjects will begin a 20-day blinded Titration Period (Day 1 to Day 20) to attain the target dose for the Maintenance Period (LCM 8mg/kg/day to LCM 12mg/kg/day, or matching PBO).

Subjects will be dispensed study medication and will begin treatment with LCM oral solution 4mg/kg/day or matching PBO for 4 days. Subjects will then be titrated at 4-day intervals as recommended in Table 7-1. The current 4-day titration step approach has been selected as it is generally accepted that frequent seizures require a rapid titration of AEDs.

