8.1.2 Baseline Period: Visit 2 (Day -3 to Day -1)

From Visit 2 (Day -3 to Day -1) to Visit 3 (Day 1), an End-of-Baseline video-EEG (up to 72 hours of continuous recording with every attempt to obtain at least 48 hours of interpretable recording) will be performed. The Day -3 assessments should be conducted prior to the start of video-EEG monitoring. The video-EEG will be conducted in an inpatient setting. Upon

completion of the End-of-Baseline video-EEG (Visits 2 and 3), the investigator will assess the electrographic seizure count and confirm the selection criteria have been met. If the subject meets all selection criteria, including the requisite number of seizures based on the End-of-Baseline video-EEG data, the subject may be randomized at Visit 3. Assessment of the video-EEG seizure count will also be performed locally by the investigator, subinvestigator, or qualified designated reader for the purpose of study analyses; however, completion of this review is not required prior to randomization.

During Visit 2, the following assessments will be performed:

- Inclusion/exclusion criteria (Day -3 only)
- Concomitant medications
- Concomitant AEDs
- VNS assessment (Day -3 only and only if applicable)
- Physical examination (brief) (Day -3 only)
- Vital signs (BP and pulse rate, including orthostatic assessments where feasible according to investigator judgment; Day -3 only)
- Body weight (Day -3 only)
- Neurological examination (brief) (Day -3 only)
- Video-EEG
- Rescue medication assessment
- AE reporting
- Review withdrawal criteria

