9 ASSESSMENT OF EFFICACY

9.1 Primary and secondary efficacy variables

The primary and secondary efficacy variables are based on the ADF of partial-onset seizures as measured on video-EEG (up to 72 hours of continuous recording with every attempt to obtain at least 48 hours of interpretable recording).

Partial-onset seizure count will be based on electrographic seizures with or without clinical correlate depending upon age as specified below.

Partial-onset seizure frequency for infants aged ≥ 1 month to ≤ 6 months will be based on electrographic seizures. Partial-onset seizure frequency for children aged >6 months to <4 years will be based on electrographic seizures with an accompanying clinical correlate.

Electrographic seizures are defined as recognizable ictal patterns on an EEG involving ≥ 2 contiguous electrodes. The seizures are initiated as a unilateral or strongly asymmetric abnormal epileptiform discharge lasting a total of >10 seconds.

The video-EEG recordings will be evaluated for seizure counts locally by the investigator, subinvestigator, or qualified designated reader.

Calculation of the Baseline Period ADF of electrographic partial-onset seizures and the Maintenance Period ADF of electrographic partial-onset seizures will be based on results from a video-EEG during each period. Subjects are expected to have at least 48 hours of interpretable video-EEG during each period. For subjects who drop out during the End-of-Maintenance Period video-EEG, the number of hours from the start of the End-of-Maintenance Period video-EEG to the time of withdrawal (in hours) will be considered for analysis. Subjects who discontinue on or before Day 20 will not require a video-EEG.

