3.2.9 Electrographic partial-onset seizures

Electrographic seizures are defined as recognizable ictal patterns on an EEG involving ≥ 2 contiguous electrodes. The seizures are initiated as a unilateral or strongly asymmetric abnormal epileptiform discharge lasting a total of > 10 seconds.

The video-EEG recordings will be evaluated locally by the investigator, sub investigator, or qualified designated reader. Subjects who discontinue on or before Day 20 will not require an End-of-Maintenance Period video-EEG.

For the purposes of this SAP, the term electrographic partial-onset seizures will be used to define electrographic partial-onset seizures with or without clinical correlate; electrographic and electroclinical partial-onset seizures will be included for subjects aged ≥1 month to ≤6 months, and electroclinical partial-onset seizures will be included for subjects aged >6 months to <4 years.

Infants aged ≥ 1 month to ≤ 6 months

Partial-onset seizure frequency for infants aged ≥1 month to ≤6 months will be based on electrographic seizures.

The total number of partial-onset seizures is calculated as the total number of type IA/IB electrographic seizures plus the total number of type IA/IB electroclinical seizures plus the total number of type IC seizures.

The total number of seizures is calculated as the total number of partial-onset seizures (as defined above) plus the total number of other seizure types reported.

Infants aged >6 months to <4 years

Partial-onset seizure frequency for infants aged >6 months to <4 years will be based on electrographic seizures with an accompanying clinical correlate.

The total number of partial-onset seizures is calculated as the total number of type IA/IB electroclinical seizures plus the total number of type IC seizures.

The total number of seizures is calculated as the total number of partial onset seizures (as defined above) plus the total number of other seizure types reported.

Calculation of the End-of-Baseline Period ADF of electrographic partial-onset seizures will be based on the results from a video-EEG (up to 72 hours of continuous recording with every attempt to obtain at least 48 hours of interpretable recording) at Visits 2 and 3. The End-of-Maintenance Period ADF of electrographic partial-onset seizures will be based on results from a video-EEG (up to 72 hours of continuous recording with every attempt to obtain at least 48 hours of interpretable recording) at Visit 6.

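### Inclusion criterion 8a omits the age rule used for the endpoint, so a child over 6 months with only electrographic seizures could be randomized with a countable baseline of zero

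*Protocol*

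**What the plan says.** - **Entry.** Protocol 6.1, criterion 8a, asks for at least two "partial-onset seizures with or without secondary generalization during the End-of-Baseline video-EEG". It then defines an electrographic seizure by electrode contiguity, by onset ("The seizures are initiated as a unilateral or strongly asymmetric abnormal epileptiform discharge lasting a total of" more than 10 seconds) and by nothing else. Clinical correlate and age are not mentioned.
- **Endpoint count.** Protocol 9.1 gives the same EEG definition and adds an age rule: "Partial-onset seizure frequency for children aged >6 months to <4 years will be based on electrographic seizures with an accompanying clinical correlate". Protocol 13.1.1 repeats it. At 6 months or younger, electrographic seizures count on their own. SAP 3.2.9 applies the rule: above 6 months the partial-onset total is type IA/IB "electroclinical seizures plus the total number of type IC seizures", so electrographic-only IA/IB events are left out.
- **Confirming entry.** Under Protocol 8.1.2, once the baseline recording is complete, "the investigator will assess the electrographic seizure count and confirm the selection criteria have been met". A count for the analyses is also made locally, but "completion of this review is not required prior to randomization".
- **Zero baseline.** SAP 8.1.2.2 classes subjects with no baseline seizures as non-responders in the EU responder analysis.

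**The concern.** Eligibility and the primary endpoint should count the same events. Here the entry criterion carries half of the counting rule and the endpoint carries all of it. The age-specific half may first be applied after the child has been randomized and dosed.

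A child over 6 months whose baseline seizures are all electrographic-only would go through titration and a second inpatient video-EEG with no possibility of being a responder. The responder rate is the EU primary endpoint. It also becomes the US primary endpoint if more than 10% of subjects discontinue early. Such children pull both response rates towards zero and so shrink the difference between arms.

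**Working it through.** **Does the route exist in the text?** Take a child over 6 months with two electrographic-only IA/IB seizures on the baseline recording.

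1. Criterion 8a as worded: two partial-onset seizures meeting the EEG definition, so the child qualifies.
2. SAP 3.2.9 count: electroclinical IA/IB (0) + IC (0) = 0.
3. ADF (Protocol 13.1.1) = 0 / interpretable hours × 24 = 0. No percent reduction can be calculated.
4. SAP 8.1.2.2: non-responder, whatever happens on treatment.

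Criterion 7 (at least two partial-onset seizures in each of the 2 weeks before Visit 1) makes this less likely. It concerns history, though, and does not guarantee a countable seizure on the baseline recording.

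**The plan's own figures (Protocol 13.6).** Assumptions: response 20% placebo and 40% lacosamide, two-sided continuity-corrected chi-square test at 5%, 99 per arm. Exact power is 83.9%, against the stated approximately 83%. Enrollment: 99 / 0.86 / 0.95 = 121.2, rounded up to 122 per arm. Both reproduce.

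**Size of the dilution.** Let g be the share of all randomized subjects with a zero countable baseline, equal in both arms. The documents do not give g; 2% to 15% is an assumed range. It is also assumed that the 20% and 40% rates describe children with a countable baseline. Response rates become 0.20(1 − g) and 0.40(1 − g). These children stay in the analysis, so the number per arm after 14% dropout is 122 × 0.86 = 105.

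| g | Placebo rate | Lacosamide rate | Power, 105 per arm |
|---|---|---|---|
| 0 | 20.0% | 40.0% | 86.3% |
| 2% | 19.6% | 39.2% | 85.2% |
| 5% | 19.0% | 38.0% | 83.6% |
| 10% | 18.0% | 36.0% | 80.4% |
| 15% | 17.0% | 34.0% | 76.9% |

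Power falls to 83% at g = 5.9% and to 80% at g = 10.6%.

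**As a share of the older children.** Protocol 5.1.2 plans 122 of 244 subjects under 2 years, with at least 25 in each of three age bands. The number under 6 months is therefore between 25 and 122 − 2 × 25 = 72. Older children make up (244 − 72)/244 = 70.5% to (244 − 25)/244 = 89.8% of the trial.

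- For 83% power: 5.9/0.898 = 6.6% to 5.9/0.705 = 8.4% of older children affected.
- For 80% power: 10.6/0.898 = 11.8% to 10.6/0.705 = 15.0%.

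**With the blinded re-estimation (Protocol 13.5).**

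- Only the baseline re-read allowance raised to its 10% cap: 99 / 0.86 / 0.90 = 128 per arm, or 110 after dropout. Power at g = 10% is 82.5%.
- All three caps reached: 109 / 0.76 / 0.90 = 159.4, about 160 per arm, or 121 after dropout. Power is 86.2% at g = 10% and 83.1% at g = 15%.

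**The case against.** **One count was intended.** Criterion 8a speaks of partial-onset seizures, and 9.1 is where the protocol says how these are counted. Protocol 5.1 and Table 5-1 footnote i assign the local count "for the purpose of both assessment of eligibility and study analyses". Protocol 5.4 speaks of "electrographic partial-onset seizures with or without clinical correlate depending upon subject age", so the electrographic count in 8.1.2 need not mean electrographic-only. Protocol 13.6 treats a child who falls short on the detailed count as one who only appeared eligible. This is a fair reading of intent and it stands as such. But none of these places applies the age rule to eligibility, and sites enroll on 8a, which repeats the definition and stops.

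**It is already allowed for.** Protocol 13.6 adds 5% for children whose baseline count later proves too low, and 13.5 re-estimates that rate up to 10%. This stands in part. The allowance is described as a difference in reading the EEG, not a difference in definition. It also inflates the sample as if those children leave the analysis, whereas SAP 8.1.2.2 keeps zero-baseline children in as non-responders.

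**The per-protocol set will remove them.** It might, since inclusion-criterion deviations are a listed category in SAP 3.4. But a child who meets 8a as written has no evident deviation, and the deviation criteria are kept in a separate document.

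**The group is narrow and its size is assumed.** Both are true. A child with even one countable seizure can still respond, so only a zero count over up to 72 hours of recording matters. The documents do not say whether the planning rates already include such children; if they do, the dilution is overstated.

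**Conclusion.** The gap is real as a matter of wording, and correcting it is recommended. As written, 8a admits a child over 6 months whom the endpoint definition gives a baseline of zero, and the procedures in 8.1.2 do not prevent this.

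The consequence is dilution of unknown size in the responder analysis, equal in both arms, and not bias. Against the planned power of about 83%, nothing is lost if such children are 5% or less of the trial. Power drops below 80% only above about 10.6%, and the blinded re-estimation can recover part of any loss. These figures rest on an assumed range for g, on equal shares in the two arms, and on the 20% and 40% rates applying to children with a countable baseline. No loss is claimed for the US covariance analysis of log ADF. Infants aged 1 to 6 months are unaffected.

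**What to change.** 1. **Criterion 8a:** add one sentence stating that the two or more End-of-Baseline seizures must be of the kind counted for the child's age in section 9.1, that is, with a clinical correlate if the child is older than 6 months.
2. **Protocol 8.1.2:** add a clause requiring the site to apply that age-specific count before randomization. The full detailed review can still be finished later.
3. **SAP:** keep the rule that a zero baseline is a non-responder as primary. Optionally, add a sensitivity analysis that leaves out subjects with no countable baseline seizures. It would still show the effect if enrollment is too far advanced to change 8a.

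No recording time or visit is added. The price is that a few children over 6 months with only electrographic seizures would no longer qualify, in a trial that already finds its youngest age groups hard to enroll.
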